2.2.2 Secondary Safety Endpoints

The **secondary safety endpoint** is the incidence and severity of all adverse events (AEs) through the 12-month timepoint.

2.2.3 Primary Efficacy Endpoint

The **primary efficacy endpoint** is change from baseline to the 12-month timepoint in functional capacity as assessed by the mid-level (elbow) dimension of the PUL 1.2.

2.2.4 Secondary Efficacy Endpoints

The **secondary efficacy endpoints** include the change from baseline for the following:

- Mid-level (elbow) dimension of the PUL 1.2 at Months 3, 6, and 9 (*Month 12 is the primary endpoint*).
- Regional systolic left ventricular (LV) wall thickening as assessed by cardiac magnetic resonance imaging (MRI) at Months 6 and 12.

2.2.5 Exploratory Efficacy Endpoints

The **exploratory efficacy endpoints** include the change from baseline to each assessment timepoint for the following assessments:

- All subjects
 - High-level (shoulder) dimension of the PUL 1.2
 - High-level (shoulder) dimension of the PUL 2.0

- Mid-level (elbow) dimension of the PUL 2.0
- Distal-level (wrist and hand) dimension of the PUL 1.2
- Distal-level (wrist and hand) dimension of the PUL 2.0
- Grip strength
- Key and tip-to-tip pinch strength
- Elbow flexion strength
- Slow vital capacity (SVC), forced expiratory volume in one second (FEV₁), forced vital capacity (FVC), peak expiratory flow (PEF), maximum inspiratory pressure (MIP), maximum expiratory pressure (MEP), peak cough flow (PCF), and inspiratory flow reserve (IFR)
- LV structure and function as assessed by cardiac MRI including ejection fraction, end-diastolic volume, end-systolic volume, stroke volume, regional wall thickness, and circumferential strain
- Biomarkers may include those for muscle inflammation (osteopontin); systemic inflammation (interleukin 1 beta [IL-1 β], IL-2, -6 and -10; tumor necrosis factor alpha [TNF- α] and C-X-C motif chemokine 10 [CXCL10]); muscle damage (troponin I [cardiac, fast skeletal, slow skeletal], troponin T, creatine kinase MM isoenzyme [CK-MM], creatine kinase MB isoenzyme [CK-MB], creatine kinase [total], creatine phosphate, and creatinine); and muscle regeneration (myostatin and follistatin)
- DMD Upper Limb Patient-Reported Outcome Measures (DMD UL-PROM)
- Pediatric Outcomes Data Collection Instrument (PODCI)
- DMD Lifetime Mobility Scale (DMD-LMS)
- Resource utilization including the incidence of hospitalizations for orthopedic injury or surgery, pulmonary infections, and antibiotic usage

- Ambulatory subjects only
 - 10-Meter Walk/Run Time (10MWRT)
 - Incidence of loss of ambulation (defined by 10MWRT > 30 seconds)
 - North Star Ambulatory Assessment (NSAA)

3 STUDY DESIGN

This Phase 2, multi-center, randomized, double-blind, placebo-controlled trial will assess the safety and efficacy of allogeneic cardiosphere-derived cells (CDCs), or CAP-1002, administered as four IV infusions, one every three months, for the treatment of subjects with DMD. Subjects with a clinical diagnosis of DMD confirmed by genetic testing and evidence of skeletal muscle impairment will undergo a battery of tests and procedures during a 30-day screening period to determine eligibility based on protocol inclusion and exclusion criteria.

Eligible subjects will be prospectively randomized in stratified permuted blocks to CAP-1002 or placebo (1:1 ratio) approximately 7 days prior to the first IV infusion of IP on Day 1.

Randomization will be stratified by site and entry item score of the PUL 1.2. Subjects will undergo baseline safety and efficacy assessments ([APPENDIX A](#)) prior to the first infusion of IP (CAP-1002 or placebo). Administration of IP (Day 1) should occur within a maximum of 14 days following randomization; if a delay of more than 14 days between randomization and IP administration is unavoidable, a conversation between the Investigator and Medical Monitor

should occur to determine the need for repeat assessments prior to infusion. Subjects that are not randomized may be re-screened at the discretion of the Investigator.

Subjects will complete study assessments at Screening; Baseline (≤ 2 days prior to Day 1); Day 1; Week 4 (± 7 days); and Months 3, 6, 9, and 12 (± 14 days, each). If the subject can travel to the investigative site, blood samples will be collected at Week 6 (± 7 days) and Month 4.5 (± 14 days).

All IV infusions will be conducted in an outpatient setting at the investigative site on Day 1 and Months 3, 6, and 9. Prior to each IP infusion, medication(s) will be administered to the subject as determined by the Investigator based on the pre-treatment guidelines and/or institutional protocols to minimize the risk of potential severe allergic reactions such as anaphylaxis. Subjects will be observed in the outpatient setting for at least two hours post infusion and then discharged the same day if medically cleared by the site Investigator.

[figure not shown]
As part of these visits, subjects will complete a safety phone call 14 days (± 3 days) after each IP infusion, and if clinically indicated, an unscheduled in-person visit will be performed at the investigative site with targeted assessments based on presentation of signs and symptoms.

Blood samples for DSA testing will be collected at Baseline, Week 4, 14-30 days prior to the IP infusions scheduled for the Month 3, 6 and 9 visits, and Month 12. Blood collections for clinical laboratory and DSA testing at Week 4 and pre-dose DSA testing at Months 3, 6, and 9 will occur either at the investigative site or remotely at a designated central laboratory patient service center. Blood collection for biomarker and exploratory biomarker testing at Week 6 and Month 4.5 will be conducted for those subjects who are able to travel to the investigative site.

A schematic of the study design is displayed in [Figure 1](#).

If trial evidence suggests an appropriate risk/benefit profile of CAP-1002, Capricor, upon the recommendation of the Data Safety Monitoring Board (DSMB), will introduce an open-label extension study to offer CAP-1002 to subjects who were randomized to placebo and completed the 12-month follow-up period of the original trial.

Figure 1 Trial Design

3.1 Sample Size and Randomization

This trial will be limited to a total of 20 randomized subjects.

This is a double-blind, placebo-controlled trial. Subjects who meet all enrollment criteria will be prospectively randomized in stratified permuted blocks to CAP-1002 or placebo (1:1 ratio) via an interactive web-based response system (IWRS) accessed directly by site personnel who have been delegated this responsibility by the Principal Investigator (PI). Randomization will be stratified by site and entry item score of the PUL 1.2 at Screening (Stratum I: Score of 2 or 3; Stratum II: Score of 4 or 5). Subjects will be randomized approximately 7 days in advance of their first IP infusion (Day 1). The central randomization will be generated in SAS or comparable software using permuted random block sizes held in confidence by the statistician preparing the master randomization list.

3.2 Data Safety Monitoring Board

The DSMB will act in a senior advisory capacity to Capricor regarding data and safety matters throughout the duration of the trial. The objectives, roles and responsibilities of the DSMB, as well as the format and frequency of their meetings, are documented in the DSMB charter.

3.3 Interim Analyses

3.3.1 Interim Analysis

The interim analysis was performed [REDACTED]

The objective of the interim analysis was to evaluate demographic data for the Intent-to-Treat (ITT) Population, study drug exposure data for the Safety Population, efficacy data for the ITT Population, Modified Intent-to-Treat (mITT) Population and Per Protocol (PP) Population, and safety and adverse event data for the Safety Population. A summary of all listings and tables that were generated to support the analysis of the interim data are outlined in Section 9.2 (APPENDIX B).

The results of the interim analysis were reviewed by the DSMB. Following the interim analysis, enrollment in the trial was discontinued (Protocol Amendment 5 dated September 27, 2019). Subsequently, three additional interim analyses with updated datasets were performed and are described below.

3.3.2 Interim Plus Analysis

The interim plus analysis was performed [REDACTED]. The objective of the interim plus analysis was to further evaluate unblinded efficacy data for the ITT and PP populations. A summary of all listings and tables that were generated are outlined in Section 9.3 (APPENDIX C).

3.3.3 Interim Plus 2 Analysis

The interim plus analysis was performed on [REDACTED] The objective of the interim plus 2 analysis was to further evaluate unblinded efficacy for the ITT and PP populations and

unblinded adverse event data for the Safety Population. A summary of all listings and tables that were generated are outlined in Section 9.4 (APPENDIX D).

3.3.4 Interim Plus 3 Analysis

The interim plus analysis was performed on [REDACTED]. The objective of the interim plus 3 analysis was to further evaluate unblinded efficacy data for the ITT Population and unblinded adverse event data for the Safety Population. A summary of all listings and tables that were generated are outlined in Section 9.5 (APPENDIX E).

4 GENERAL STRATEGIES FOR DATA PRESENTATION

Data with qualifiers (e.g., “<”) will be listed with the qualifier but summarized without the qualifier. Subject data listings will include data collected for all subjects. Listings will be sorted by treatment, site, subject number, nominal visit, date and time (as applicable), unless otherwise indicated.

Categorical analyses will be summarized using counts and percentages. Percentages will be based on the number of subjects in the analysis set for whom there are non-missing data, unless otherwise specified. Continuous variables, including change from baseline, will be summarized using descriptive statistics [n, mean, standard deviation (SD), median, minimum, maximum].

All statistical comparisons will be performed using two-sided tests at $\alpha=0.05$ significance level, unless specifically stated otherwise. P-values will be presented to four decimal places. P-values <0.0001 will be presented as “< 0.0001.”

All analyses will be performed using SAS v 9.3 or higher (SAS Institute, Inc, Cary, North Carolina, USA). Validation and quality control of the tables, listings and figures (TLFs) will follow the appropriate [REDACTED] standard operating procedures (SOPs).

4.1 Treatment Groups

The treatment groups to be presented will be those who receive CAP-1002, those who receive placebo, and all subjects (as applicable).

4.2 Study Day

The day of first IP administration is defined as Day 1. All other study days will be labeled relative to Day 1. Thus, study day for a particular event date on or after Day 1 is calculated as: $(Date\ of\ event - Date\ of\ first\ IP\ administration + 1)$. An event that occurs prior to Day 1 is calculated as: $(Date\ of\ event - Date\ of\ IP\ administration)$.

The duration of an event will be calculated as $(Event\ end\ date - Event\ start\ date + 1)$. Day 0 will not be used.

The baseline value for each subject is the last non-missing value obtained prior to the time of the first IP administration on Day 1.

4.3 Handling of Dropouts or Missing Data

Subject-level listings will present data as reported. Missing or partially missing dates that are required for date-dependent definitions (e.g., treatment-emergent adverse events (TEAEs), concomitant medications) will be assumed to be the most conservative date possible.

For the primary efficacy endpoint, no imputation will be performed and the mixed-model repeated measures (MMRM) analysis will use all available data to estimate the mean treatment effect.

An AE with a completely missing start date will be considered treatment-emergent; similarly, an AE that started the same month and year as IP administration but with missing start day will be considered treatment-emergent.

AEs with missing seriousness will be counted as “serious” in tables and missing in listings; likewise, AEs with missing severity will be counted as “severe” in tables and missing in listings, and AEs with missing relatedness to the IP and/or IP administration procedure will be counted as “possible” and missing in listings.

Medical history with missing stop dates will be considered ongoing. Medications with missing stop dates will be considered in concurrent use during the study and counted in the summary table of concomitant medications unless the start date is after the last IP administration.

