12.4. Prior and Concomitant Medications

All medications taken within one month prior to the screening visit through trial completion will be captured. Medications will be reviewed at each trial visit and any medication changes, including new and discontinuations, will be recorded.

For each medication, generic name, indication, dose, frequency, route, and starting and stopping dates/times (if applicable) will be collected. The trade name of the medication is to be reported for combination therapies (e.g., Alka-Seltzer, Advair, etc.).

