5.9 Prior and Concomitant Medications

Prescription, over-the-counter, and alternative medication use will be coded to drug class, preferred drug name, and generic/trade drug name using the World Health Organization Drug Global dictionary (WHODrug Global) version September 1, 2017. Medications that were stopped before the start of the IP administration procedure will be considered “pre-treatment.” All other medications will be considered “concomitant.” Medications that were started or ongoing at the time the IP administration procedure was started will be considered “baseline” (a subset of “concomitant”). Pre-treatment, baseline, and concomitant medications will be listed separately.

Frequencies and percentages of subjects reporting or receiving cardiac and steroid medications will be summarized by WHODrug Global Anatomic Therapeutic Chemical (ATC) Level 2 and Preferred Term. Pre-treatment and baseline cardiac and steroid medications will be summarized separately from concomitant cardiac and steroid medications.

At each level of subject summarization, subjects who reported one or more medication within that level are only counted once for that level.

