3.2. Cardiac and Steroid Medications

Frequencies and percentages of subjects reported or receiving WHODrug Global cardiac medications at any time on or after Day 1 (date of first IP exposure) will be both summarized by WHODrug Global Anatomic Therapeutic Chemical (ATC) Level 2 and Preferred Term and listed.

Frequencies and percentages of subjects reported or receiving WHODrug Global steroid medications at any time on or after Day 1 (date of first IP exposure) will be summarized separately for systemic use and non-systemic use, where steroid medications with reported

indications as DMD, DMD treatment, or SOC for DMD are considered for systemic use, and steroid medications with other indications are considered for non-systemic use. Both summaries will be presented by WHODrug Preferred Term. All steroid medications on study, along with their reported indications, will be listed.

4. Pharmacoeconomic Analysis

An exploratory analysis was planned to explore all-cause hospitalizations, hospitalizations for orthopedic injury/surgery or pulmonary infections, and antibiotic usage. Billing information was not to be collected; rather, standardized, composite or bundled costings of national averages was planned to be used in the analysis. Given the small sample size and minimal observations on trial, this analysis was not completed.

References

1. Siegel S. Nonparametric Statistics. Am Stat 1957;11(3):13–9.
2. Mallinckrodt CH. and Ilya Lipkovich. A practical guide to analyzing longitudinal clinical trial data. CRC Press. Boca Raton. 2017 (Chapter 11).
3. O'Brien PC. Procedures for comparing samples with multiple endpoints. Biometrics 1984; 40: 1079-87.

Signature Approval of SAP Addendum – Post Hoc Analysis HOPE-2 Study

A Phase 2, Randomized, Double-Blind, Placebo-Controlled Trial Evaluating the Safety and Efficacy of Intravenous Delivery of Allogeneic Cardiosphere-Derived Cells in Subjects with Duchenne Muscular Dystrophy (HOPE-2)

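### SAP 4.3 leaves out of the concomitant-medication table any medicine with no stop date that started after the last infusion, contrary to SAP 5.9, Protocol 14.4.3 and Addendum 3.2

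*SAP*

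**What the plan says.** SAP 4.3 (Handling of Dropouts or Missing Data) first sets a general principle: a missing or partial date needed for a date-dependent definition "will be assumed to be the most conservative date possible". It then gives a rule for medications. One that lacks a stop date is presumed to have been in use on study, with an exception for late starts: it is "counted in the summary table of concomitant medications unless the start date is after the last IP administration".

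SAP 5.9 (Prior and Concomitant Medications) divides all medications in two. "Medications that were stopped before the start of the IP administration procedure will be considered “pre-treatment", and "All other medications will be considered “concomitant". Protocol 14.4.3 gives the same definitions. Neither sets an upper limit at the last infusion. SAP 5.9 plans frequency tables for cardiac and steroid medicines only: "Pre-treatment and baseline cardiac and steroid medications will be summarized separately from concomitant cardiac and steroid medications". All medications are listed.

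Protocol 12.4 sets the collection period: "All medications taken within one month prior to the screening visit through trial completion will be captured".

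Section 3.2 of the post hoc SAP Addendum summarizes cardiac and steroid medicines taken "at any time on or after Day 1 (date of first IP exposure"). Its introduction says that these summaries are set out in more detail there. It does not withdraw the SAP 4.3 exception, and it gives no rule of its own for a missing stop date.

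**The concern.** A missing stop date leaves open when use ended. It casts no doubt on when use began. If the start date is known and falls between the last infusion and Month 12, the medicine was taken on study, and the missing stop date is no reason to leave it out. The exception therefore removes records that SAP 5.9 and Protocol 14.4.3 call concomitant.

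It also selects in an odd direction. A short course begun after Month 9 with a recorded end is outside the exception and is counted. A lasting treatment begun at the same time with no end date is dropped. For a reader who wants to know whether background therapy changed before the Month 12 assessment, the second record is the more informative.

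At stake is the by-arm count of cardiac and steroid medicines, the only medication classes that SAP 5.9 tabulates. The table is small: with 20 subjects randomized 1:1, and assuming about 10 per arm, one subject left out moves an arm's percentage by 1/10, or 10 percentage points.

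**Working it through.** The plan states no figure on this point, so there is nothing to reproduce. The check has two parts: each kind of record set against each rule, and visit-day arithmetic for the period at risk.

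**Records against rules** (start date known and on study)

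| Start | Stop date | SAP 4.3 | SAP 5.9 and Protocol 14.4.3 | Addendum 3.2 (cardiac or steroid) |
|---|---|---|---|---|
| Day 1 to last infusion | recorded | rule does not apply | concomitant | counted |
| Day 1 to last infusion | missing | counted | concomitant | counted |
| after last infusion | recorded | rule does not apply | concomitant | counted |
| after last infusion | missing | **not counted** | concomitant | counted |

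Only the last row conflicts. Such a record was not stopped before IP, so it is not pre-treatment. It was neither started nor ongoing when IP administration began, so it is not baseline. Under SAP 4.3 it is not counted as concomitant either, so it falls into no tabulated class, although the SAP 5.9 scheme is meant to be exhaustive.

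**Period at risk**

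Inputs: infusions on Day 1 and Months 3, 6 and 9 (Protocol 7.1); nominal days 90, 180, 270 and 360 for Months 3, 6, 9 and 12, each ±14 days (Protocol Table 3).

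- Fully dosed subject, nominal: 360 − 270 = 90 days.
- Shortest: (360 − 14) − (270 + 14) = 346 − 284 = 62 days.
- Longest: (360 + 14) − (270 − 14) = 374 − 256 = 118 days.
- Share of the nominal study period: 90 / (360 − 1) = 90/359, about 25%.

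If infusions stop early and the subject is followed to Month 12:

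| Last infusion | Nominal | Within windows |
|---|---|---|
| Month 6 | 360 − 180 = 180 days | 152 to 208 |
| Month 3 | 360 − 90 = 270 days | 242 to 298 |
| Day 1 | 360 − 1 = 359 days | 345 to 373 |

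The early-stopping figures are upper cases. Protocol 8.4 also allows a subject withdrawn for an acute reaction or other safety issue to be followed for at least 3 months after the last infusion instead of to Month 12.

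**What must hold for a table count to change**

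The record must have no stop date, must start after the last infusion, and must be a cardiac or steroid medicine. SAP 5.9 counts a subject once at each level of summarization, so the record must also add a Preferred Term or ATC Level 2 class that the subject does not already contribute.

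**With the exception removed**

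The last row of the first table becomes counted under SAP 4.3, the period at risk falls to 0 days, and the four provisions agree.

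**The case against.** The strongest reply is that the Addendum has already dealt with this. SAP 5.9 tabulates only cardiac and steroid medicines, and for those classes Addendum 3.2 counts any use from Day 1, which includes starts after the last infusion. That largely stands. What remains is that the Addendum neither withdraws the exception nor supplies a missing-stop-date rule. A programmer could apply SAP 4.3 to one table and not the other, or carry it into both.

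The second reply is that nothing inferential depends on it. That stands in full. The tables are descriptive, the MMRM in SAP 6.1 has no medication term, and the listings show data as reported.

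The exception might also be defended as a deliberate on-treatment definition. That does not fit the text, because a medicine started after the last infusion with a recorded stop date is still counted.

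Four stronger readings are tempting, and the documents do not support them:

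- *All new treatment after Month 9 goes uncounted.* Only records without a stop date do. The 25% is the share of the calendar in which such a record could arise, not a share of data lost.
- *A late steroid dose change would be hidden by the exception.* Inclusion criterion 8 requires prior systemic glucocorticoid. A dose change within the same Preferred Term would not alter the table, with or without the exception; only a switch to a different term could.
- *The arms would be affected unequally because reactions stop dosing more often on CAP-1002.* The cut-off does depend on treatment actually received, but the readable text gives no reaction or stopping rate by arm.
- *Every ongoing medicine is affected.* Protocol 12.4 asks for stop dates where applicable. The documents do not say whether an ongoing entry counts as a missing stop date.

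**Conclusion.** The inconsistency is real and narrow. For a medicine with no stop date that begins after the last infusion, SAP 4.3 gives a different count from SAP 5.9, Protocol 14.4.3 and, for cardiac and steroid medicines, Addendum 3.2. It also runs against the conservative-date principle in its own section. Such records can arise over a nominal 90 days in a fully dosed subject, and over longer periods in subjects who stop infusions early and remain in follow-up.

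The number of affected records cannot be known from the documents and may be zero. How often the exception applies depends on how ongoing entries are coded, which is not stated. The 10-percentage-point figure assumes about 10 subjects per arm and one subject whose only qualifying record is excluded. The effect is confined to a descriptive table, so this is a low-priority correction.

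**What to change.** In SAP 4.3, delete the exception, or replace it with *unless the start date is after the subject's Month 12 or early-termination visit*. Add that medication entries marked as ongoing follow the same rule. State that this one rule governs both the SAP 5.9 and the Addendum 3.2 tables, so that their counts of the same medicines agree.

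Optionally, add a by-arm row for cardiac and steroid medicines started after the last infusion. This would be an extra display; the correction does not need it.

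The cost is two or three sentences and a re-run of the medication tables. No new data are needed, because Protocol 12.4 already collects medications to the end of the trial.
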